13.2 Interim Analysis and Criteria for Early Termination

No interim analysis is planned.

13.3 Determination of Sample Size

Justification of Sample size

Within the subjects who recorded maximum NRS score of ≥ 4 during 1 menstrual cycle just before the start of the Treatment drug administration in the TAK-385 phase 2 study in Japanese patients with uterine fibroids, the proportion of subjects with a maximum NRS score of 1 or less during the 28 days before the final dose of study drug was 14.7% (5/34) in placebo group and 75.9% (22/29) in TAK-385 40 mg group.

A sample size of 28 per group would give a power of $>90\%$ when a Fisher's exact test with a significance level of 5% (2-sided) is used for the comparison between TAK-385 40 mg group

CONFIDENTIAL

and placebo group, under the assumption that “the proportion of subjects with a maximum NRS score of 1 or less during the 28 days before the final dose of study drug” is 20.0% for placebo group and 65.0% for TAK-385 40 mg group (SAS ver.9.2 Power procedure).

Based on the above, 28 subjects are considered sufficient for the number of evaluable subjects per group. Thirty two subjects are to be randomized to each group on the assumption that some subjects will be excluded from the analysis of the primary endpoint.

14.0 QUALITY CONTROL AND QUALITY ASSURANCE

14.1 Study-Site Monitoring Visits

Monitoring visits to the study site will be made periodically during the study to ensure that all aspects of the protocol are followed. Source documents will be reviewed for verification of data recorded on the eCRFs. Source documents are defined as original documents, data, and records. The investigator and institution guarantee access to source documents by the sponsor or its designee (contract research organization [CRO]) and by the IRB.

All aspects of the study and its documentation will be subject to review by the sponsor or designee (as long as blinding is not jeopardized), including but not limited to the Investigator's Binder, study medication, subject medical records, informed consent documentation, and review of eCRFs and associated source documents. It is important that the investigator, subinvestigator and other study personnel are available during the monitoring visits and that sufficient time is devoted to the process.

14.2 Protocol Deviations

The investigator or subinvestigator can deviate and change from the protocol for any medically unavoidable reason, for example, to eliminate an immediate hazard to study subjects, without a prior written agreement with the sponsor or a prior approval from IRB. In the event of a deviation or change, the principal investigator should notify the sponsor and the head of the site of the deviation or change as well as its reason in a written form, and then retain a copy of the written form. When necessary, the principal investigator may consult and agree with the sponsor on a protocol amendment. If the protocol amendment is appropriate, the amendment proposal should be submitted to the head of the site as soon as possible and an approval from IRB should be obtained.

The investigator or subinvestigator should document all protocol deviations.

14.3 Quality Assurance Audits and Regulatory Agency Inspections

The study site also may be subject to quality assurance audits by the sponsor or designees. In this circumstance, the sponsor-designated auditor will contact the site in advance to arrange an auditing visit. The auditor may ask to visit the facilities where laboratory samples are collected, where the medication is stored and prepared, and any other facility used during the study. In addition, there is the possibility that this study may be inspected by regulatory agencies, including those of foreign governments (eg, the Food and Drug Administration [FDA], the United Kingdom Medicines and Healthcare products Regulatory Agency[MHRA], the Pharmaceuticals and Medical Devices Agency of Japan[PMDA]). If the study site is contacted for an inspection by a regulatory body, the sponsor should be notified immediately. The investigator and institution guarantee access for quality assurance auditors to all study documents as described in Section 14.1.

15.0 ETHICAL ASPECTS OF THE STUDY

This study will be conducted with the highest respect for the individual participants (ie, subjects) according to the protocol, the ethical principles that have their origin in the Declaration of Helsinki, and the ICH Harmonised Tripartite Guideline for GCP. Each investigator will conduct the study according to applicable local or regional regulatory requirements and align his or her conduct in accordance with the “[Responsibilities of the Investigator](#)” that are listed in [Appendix D](#). The principles of Helsinki are addressed through the protocol and through appendices containing requirements for informed consent and investigator responsibilities.

15.1 IRB Approval

IRBs must be constituted according to the applicable local requirements. The sponsor or designee will require documentation noting all names and titles of members who make up the respective IRB. If any member of the IRB has direct participation in this study, written notification regarding his or her abstinence from voting must also be obtained.

The sponsor or designee will supply relevant documents for submission to the respective IRB for the protocol’s review and approval. This protocol, the Investigator’s Brochure, a copy of the informed consent form, and, if applicable, subject recruitment materials and/or advertisements and other documents required by all applicable laws and regulations, must be submitted to a central or local IRB for approval. The IRB’s written approval of the protocol and subject informed consent must be obtained and submitted to the sponsor or designee before commencement of the study (ie, before shipment of the sponsor-supplied drug or study specific screening activity). The IRB approval must refer to the study by exact protocol title, number, and version date; identify versions of other documents (eg, informed consent form) reviewed; and state the approval date. The sponsor will notify site once the sponsor has confirmed the adequacy of site regulatory documentation. Until the site receives notification no protocol activities, including screening may occur.

Sites must adhere to all requirements stipulated by their respective IRB. This may include notification to the IRB regarding protocol amendments, updates to the informed consent form, recruitment materials intended for viewing by subjects, local safety reporting requirements, reports and updates regarding the ongoing review of the study at intervals specified by the respective IRB, and submission of the investigator’s final status report to IRB. All IRB approvals and relevant documentation for these items must be provided to the sponsor or its designee.

Subject incentives should not exert undue influence for participation. Payments to subjects must be approved by the IRB and sponsor.

Regarding PGx investigation using collected and stored specimens, analysis will be carried out at the time when detail is determined. The sponsor will create a research protocol for PGx investigations and a research protocol will require prior approval of the company IRB in Japan.

15.2 Subject Information, Informed Consent, and Subject Authorization

Written consent documents will embody the elements of informed consent as described in the Declaration of Helsinki and the ICH Guidelines for GCP and will be in accordance with all

CONFIDENTIAL

applicable laws and regulations. The informed consent form describes the planned and permitted uses, transfers, and disclosures of the subject's personal and personal health information for purposes of conducting the study. The informed consent form further explains the nature of the study, its objectives, and potential risks and benefits, as well as the date informed consent is given. The informed consent form will detail the requirements of the participant and the fact that she is free to withdraw at any time without giving a reason and without prejudice to her further medical care.

The investigator is responsible for the preparation, content, and IRB approval of the informed consent form. The informed consent form must be approved by the IRB prior to use.

The informed consent form must be written in a language fully comprehensible to the prospective subject. It is the responsibility of the investigator or subinvestigator to explain the detailed elements of the informed consent form to the subject. Information should be given in both oral and written form whenever possible and in the manner deemed appropriate by the IRB.

The subject must be given ample opportunity to: (1) inquire about details of the study and (2) decide whether or not to participate in the study. If the subject determines she will participate in the study, then the informed consent form must be signed and dated by the subject at the time of consent and prior to the subject entering into the study. The subject should be instructed to sign using their legal names, not nicknames, using blue or black ballpoint ink. The investigator or subinvestigator must also sign and date the informed consent form at the time of consent and prior to subject entering into the study.

Once signed, the original informed consent form will be stored in the investigator's site file. The investigator or subinvestigator must document the date the subject signs the informed consent in the subject's medical record. Copies of the signed informed consent form shall be given to the subject.

All revised informed consent forms must be reviewed and signed by relevant subjects in the same manner as the original informed consent. The date the revised consent was obtained should be recorded in the subject's medical record, and the subject should receive a copy of the revised informed consent form.

PGx research should be explained to the subject using "Informed Consent Form for PGx research of TAK-385" after explanation about the study using the informed consent form has been given. Specimens for PGx research should be collected from subjects who consented to participate in the study and PGx research.

The procedure specified in Section 9.4 should be followed when a subject requests disposal of her PGx samples.

15.3 Subject Confidentiality

The sponsor and designees affirm and uphold the principle of the subject's right to protection against invasion of privacy. Throughout this study, a subject's source data will only be linked to the sponsor's clinical study database or documentation via a unique identification number. As permitted by all applicable laws and regulations, limited subject attributes, such as sex, age, or

date of birth may be used to verify the subject and accuracy of the subject's unique identification number.

To comply with ICH Guidelines for GCP and to verify compliance with this protocol, the sponsor requires the investigator to permit its monitor or designee's monitor, representatives from any regulatory authority (eg, FDA, MHRA, PMDA), the sponsor's designated auditors, and the appropriate IRBs to review the subject's original medical records (source data or documents), including, but not limited to, laboratory test result reports, ECG reports, admission and discharge summaries for hospital admissions occurring during a subject's study participation, and autopsy reports. Access to a subject's original medical records requires the specific authorization of the subject as part of the informed consent process (see Section 15.2).

Copies of any subject source documents that are provided to the sponsor must have certain personally identifiable information removed (ie, subject name, address, and other identifier fields not collected on the subject's eCRF).

15.4 Publication, Disclosure, and Clinical Trial Registration Policy

15.4.1 Publication and Disclosure

The investigator is obliged to provide the sponsor with complete test results and all data derived by the investigator from the study. During and after the study, only the sponsor may make study information available to other study investigators or to regulatory agencies, except as required by law or regulation. Except as otherwise allowable in the clinical study site agreement, the protocol or study results are the sole responsibility of the sponsor.

The sponsor may publish any data and information from the study (including data and information generated by the investigator) without the consent of the investigator.

The investigator and subinvestigator need to obtain a prior written approval from the sponsor to publish any information from the study externally such as to a professional association.

15.4.2 Clinical Trial Registration

In order to ensure that information on clinical trials reaches the public in a timely manner and to comply with applicable laws, regulations and guidance, Takeda will, at a minimum register interventional clinical trials it sponsors anywhere in the world on ClinicalTrials.gov or other publicly accessible websites before start of study, as defined in Takeda Policy/Standard. Takeda contact information, along with investigator's city, country, and recruiting status will be registered and available for public viewing.

15.4.3 Clinical Trial Results Disclosure

Takeda will post the results of clinical trials on ClinicalTrials.gov or other publicly accessible websites, as required by Takeda Policy/Standard, applicable laws and/or regulations.

15.5 Insurance and Compensation for Injury

Each subject in the study must be insured in accordance with the regulations applicable to the site where the subject is participating. If a local underwriter is required, then the sponsor or sponsor's designee will obtain clinical study insurance against the risk of injury to clinical study subjects. Refer to the Clinical Study Site Agreement regarding the sponsor's policy on subject compensation and treatment for injury. If the investigator and subinvestigator have questions regarding this policy, he or she should contact the sponsor or sponsor's designee.

3.0 LIST OF ABBREVIATIONS

AE	adverse event
AESI	adverse event of special interest
ALP	alkaline phosphatase
ALT	alanine aminotransferase
AST	aspartate aminotransferase
AUC	area under the blood concentration-time curve
BMD	bone mineral density
BMI	body mass index
BUN	blood urea nitrogen
Cmax	maximum observed plasma concentration
CRF	case report form
CRO	contract research organization
CT	computed tomography
E2	estradiol
ECG	electrocardiogram
eCRF	electronic case report form
FAS	full analysis set
FDA	Food and Drug Administration
Fe	iron
FSH	follicle-stimulating hormone
GCP	Good Clinical Practice
GGT	gamma glutamyl transferase
GnRH	gonadotropin-releasing hormone
HGB	hemoglobin
HDL	high density lipoprotein
hCG	human chorionic gonadotropin
HCT	hematocrit
ICH	International Conference on Harmonisation
INN	international non-proprietary name
INR	international normalized ratio
IRB	institutional review board
IUD	intrauterine device
LDH	lactate dehydrogenase
LDL	low density lipoprotein
LFT	liver function test
LH	luteinizing hormone
MedDRA	Medical Dictionary for Regulatory Activities
MHRA	Medicines and Healthcare products Regulatory Agency
MRI	magnetic resonance imaging
NILM	negative for intraepithelial lesion or malignancy

NRS	numerical rating scale
NSAIDs	non-steroidal anti-inflammatory drugs
P	progesterone
PBAC	pictorial blood loss assessment chart
P-gp	P-glycoprotein
PGx	pharmacogenomics
PMDA	Pharmaceuticals and Medical Devices Agency
PPS	per protocol set
PT	preferred term
PTE	Pretreatment event
QOL	quality of life
RBC	red blood cell
Run-in AE	run-in adverse event
SAE	serious adverse event
SAP	statistical analysis plan
SC	subcutaneous(ly)
SERM	selective estrogen receptor modulator
SOC	system organ class
SUSARs	suspected unexpected serious adverse reactions
TEAE	treatment-emergent adverse event
TPC	Takeda Pharmaceutical Company Limited
UFS-QOL	uterine fibroid symptom and quality of life
ULN	upper limit of normal
WBC	white blood cell
WHO	World Health Organization

4.0 OBJECTIVES

4.1 Primary Objective

The primary objective of this study is to evaluate the efficacy of TAK-385 40 mg administered orally once daily for 12 weeks, compared with placebo in subjects having pain symptoms associated with uterine fibroids.

4.2 Secondary Objective

The secondary objective of this study is to evaluate the safety of TAK-385 40 mg administered orally once daily for 12 weeks, compared with placebo in subjects having pain symptoms associated with uterine fibroids.

4.3 Additional Objectives

An additional objective of this study is to evaluate the pharmacodynamic effect, which is blood concentrations of luteinizing hormone (LH), follicle-stimulating hormone (FSH), estradiol (E₂), and progesterone (P).

4.4 Study Design

An overview of the study design is shown in Figure 4.

4.4.1 Study Population and Design

This is a phase 3, multicenter, randomized, double-blind, parallel-group study to evaluate the efficacy of TAK-385 40 mg administered orally once daily for 12 weeks compared with placebo in subjects having pain symptoms associated with uterine fibroids.

Subjects must have a diagnosis of uterine fibroids confirmed by transvaginal ultrasound or other methods. Subjects must experience pain symptoms (eg, lower abdominal pain and low back pain) with intensity of ≥ 1 on the numerical rating scale (NRS) score for at least 2 days during 1 menstrual cycle, of which at least one of the intensities should be at least moderate (NRS score of ≥ 4). The total number of subjects to be randomized under double-blind conditions is 64 (32 subjects each for the TAK-385 40 mg group or placebo group).

[figure not shown]
After signing the informed consent form, subjects will start recording in the patient diary from the day of VISIT 1. During the period between VISIT 2 and VISIT 3, in which subjects must experience 1 menstrual cycle, the baseline values for the efficacy evaluation of pain symptoms (baseline NRS score: the maximum NRS score for the entire menstrual cycle immediately before VISIT 3.) will be collected. Subjects should record in the patient diary every day until the end of study drug administration. VISIT 2 should be between the first and fifth day of the first menstruation after VISIT 1. The study drug (TAK-385 placebo) will be administered under single-blind conditions from the day of first menstruation after VISIT 1 to the day before VISIT 3. VISIT 3 should be between the first and fifth day of the second menstruation after VISIT 1. From VISITS 2 to 6, subjects should try to visit the study site during the morning in a fasted state and before taking the study drug.

This study consists of Screening of approximately 1 to 6 weeks, a Run-in period of 3 to 6 weeks, a Treatment period of 12 weeks, and a Follow-up period of 4 weeks. The total period of study participation is approximately 20 to 28 weeks. If the recovery of the first post-treatment menstruation is not observed by the visit at the end of the Follow-up (VISIT 7), the subject will undergo further follow-up using possible means such as by telephone interview, until the recovery of the first post-treatment menstruation is observed. During the course of this study, subjects will visit the study site to undergo the designated examinations and evaluations at each visit.

4.4.2 Dose Level and Regimen

At VISIT 3, subjects will be randomized in a 1:1 ratio to either the TAK-385 40 mg group or placebo group. Study drug (TAK-385 40 mg or TAK-385 placebo) will be administered from the day of VISIT 3 to the day before VISIT 6 (or until early termination) under double-blind conditions.

Figure 4 Schematic of Study Design

* In addition to Day -80~ -26, informed consent may be obtained before Day -80.

**VISIT 2 and 3: On days 1 to 5 of the menstrual cycle

5.0 ANALYSIS ENDPOINTS

5.1 Primary Endpoint

Proportion of subjects with a maximum NRS (an 11-point scale for patient self-reporting of pain symptoms. The score ranges from 0 to 10.) score of 1 or less during the 28 days before the final dose of study drug

5.2 Secondary Endpoints

- 1) Efficacy:
 - Proportion of subjects with a maximum NRS score of 0 during the 28 days before the final dose of study drug
 - Mean NRS score during the 28 days before the final dose of study drug
 - Number of days without pain symptoms (NRS = 0) during the 28 days before the final dose of study drug
- 2) Safety:
 - Adverse events (AEs), vital signs, weight, standard 12-lead electrocardiogram (ECG), clinical laboratory tests

5.3 Additional Endpoints

- Proportion of days using analgesics during the 28 days before the final dose of study drug LH, FSH, E₂ and P (Week 4, 8, 12 and Follow-up)

6.0 DETERMINATION OF SAMPLE SIZE

Within the subjects who recorded maximum NRS score of ≥ 4 during 1 menstrual cycle just before the start of the Treatment drug administration in the TAK-385 phase 2 study in Japanese patients with uterine fibroids, the proportion of subjects with a maximum NRS score of 1 or less during the 28 days before the final dose of study drug was 14.7% (5/34) in placebo group and 75.9% (22/29) in TAK-385 40 mg group.

A sample size of 28 per group would give a power of $>90\%$ when a Fisher's exact test with a significance level of 5% (2-sided) is used for the comparison between TAK-385 40 mg group and placebo group, under the assumption that "the proportion of subjects with a maximum NRS score of 1 or less during the 28 days before the final dose of study drug" is 20.0% for placebo group and 65.0% for TAK-385 40 mg group (SAS ver.9.2 Power procedure).

Based on the above, 28 subjects are considered sufficient for the number of evaluable subjects per group. Thirty two subjects are to be randomized to each group on the assumption that some subjects will be excluded from the analysis of the primary endpoint.

7.0 METHODS OF ANALYSIS AND PRESENTATION

7.1 General Principles

All statistical analyses will be conducted using SAS® Version 9.2, or higher.

A statistical test for the primary endpoint will be reported as 2-sided and will be assessed at $\alpha=0.05$ significance level and all confidence intervals will be reported as 2-sided unless otherwise stated. P-values will be rounded to 4 decimal places prior to assessment of statistical significance.

Means and medians will be presented to 1 more decimal place than the recorded data. The standard deviations (SDs) will be presented to 2 more decimal places than the recorded data. Confidence intervals about a parameter estimate will be presented using the same number of decimal places as the parameter estimate.

Where appropriate, variables will be summarized descriptively by study visit. For the categorical variables, the count and proportions of each possible value will be tabulated by treatment group. The denominator for the proportion will be based on the number of subjects who provided non-missing responses to the categorical variable. For continuous variables, the number of subjects with non-missing values, mean, median, SD, minimum, and maximum values will be tabulated. Confidence intervals for continuous variables will be calculated based on t-statistics and ones for categorical variables will be based on Wald confidence intervals without using any model, unless otherwise stated.

7.1.1 Study Definitions

Duration of exposure to double-blind study drug (days):

Date of last dose of double-blind study drug - date of first dose of double-blind study drug +
1

Double-blind study drug compliance (%):

Number of double-blind study drugs taken/duration of exposure to double-blind study drug*
100 (rounded to 1 decimal places)

Disease Duration (years):

((year of informed consent*12 + month of informed consent) -(year of first defined diagnosis of uterine fibroids*12 + month of first defined diagnosis of uterine fibroids))/12 (rounded to 1 decimal places)

Maximum Drug Holidays (days):

Maximum number of consecutive days on which the subject does not take the study drug for the treatment period

Proportion of subjects with a maximum NRS score of 1 or less during the 28 days before the final dose of study drug

CONFIDENTIAL

((number of subjects with a maximum NRS score of 1 or less during the last 28 days of the treatment)/(number of subjects with available data during the 27 days before the final dose of study drug and the date))*100 (rounded to 1 decimal places)

Similarly, for proportion of subjects with a maximum NRS score of 0 during the 27 days before the final dose of study drug and the date, its numerator will be defined as number of subjects with a maximum NRS score of 0 during the 27 days before the final dose of study drug and the date.

Number of days without pain symptoms (NRS = 0) during the 28 days before the final dose of study drug (%):

((number of days without pain symptoms (NRS = 0) during the last 28 days of the treatment)/(number of days with available data during the last 28 days of the treatment))*100 (rounded to 1 decimal places)

Maximum NRS score at baseline

Maximum NRS score from first day of menstrual period confirmed at Visit 2 to a day prior to menstrual period confirmed at Visit 3

Mean NRS score at baseline

Mean NRS score from first day of menstrual period confirmed at Visit 2 to a day prior to menstrual period confirmed at Visit 3

Maximum NRS score from Day 1 to 28, 29 to 56, and 57 to 84

Maximum NRS score from Day 1 to earlier of Day 28 or Follow-up Day 3.

Similarly, Maximum NRS score from Day 29 to 56 and from Day 57 to 84 will be defined as maximum NRS score from Day 29 to earlier of Day 56 or Follow-up Day 3 and from Day 57 to earlier of Day 84 or Follow-up Day 3, respectively.

Mean NRS score from Day 1 to 28, 29 to 56, and 57 to 84

Mean NRS score from Day 1 to earlier of Day 28 or Follow-up Day 3.

Similarly, Mean NRS score from Day 29 to 56 and from Day 57 to 84 will be defined as mean NRS score from Day 29 to earlier of Day 56 or Follow-up Day 3 and from Day 57 to earlier of Day 84 or Follow-up Day 3, respectively.

Number of days without pain symptoms (NRS = 0) from Day 1 to 28, 29 to 56, and 57 to 84

((number of days without pain symptoms (NRS = 0) from Day 1 to earlier of Day 28 or Follow-up Day 3)/(number of days with available data from Day 1 to earlier of Day 28 or Follow-up Day 3))*100 (rounded to 1 decimal places)

Number of days without pain symptoms (NRS = 0) from Day 29 to 56 and from Day 57 to 84 will be derived in a similar manner.

Use of analgesic medications during the 28 days before the final dose of study drug

((number of days with analgesic medications use during the last 28 days of the treatment)/(number of days with available data during the last 28 days of the treatment))*100 (rounded to 1 decimal places)

Myoma volumes

$$D1*D2*D3*\pi/6 \text{ (cm}^3\text{)}$$

Definitions of D1, D2 and D3 are shown in protocol.

Uterine volumes will be similarly calculated.

Duration of Menstruation Recovery

Date of menstruation recovery - date of last dose of double-blind study drug

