9.1.18 Status of Menstruation Recovery

If the first menstruation after the end of study drug administration is observed before the VISIT 7 in the Follow-up, the date of onset of the first menstruation is recorded in the eCRF. If menstruation recovery is not observed by the VISIT 7 in the Follow-up, follow-up will be continued as far as possible through telephone calls or other means until the recovery of the first menstruation. If menstruation recovery is observed during continued follow-up, the date of recovery should be recorded in the eCRF. The status at the end of menstruation follow-up will be recorded in the eCRF regarding menstruation recovery. After the Follow-up, follow-up will not be continued in subjects who undergo surgery or receive hormone therapy for the treatment of uterine fibroids before the recovery of menstruation.

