7.1.4 Methods for Handling Missing Data

All available efficacy and safety data will be included in data listing and tabulations. No imputation of values for missing data will be performed unless otherwise specified.

- For UFS-QoL, published scoring manuals and guidelines will be used to calculate UFS-QoL and handle missing data (see Appendix 3).
- For myoma or uterus volume, if D1 and D2 of the myoma or uterus are present but D3 is missing, then the volume will be calculated as $D1*D2*D2*\pi/6$ (cm^3).
- For LH, FSH, E₂, P and clinical laboratory tests, values less than the lower limit of quantification will be treated as zero when calculating the descriptive statistics.

- Disease duration with first diagnosis date of uterine fibroid that are completely or partially missing will be derived as follows:
 1. If the year is missing, then the disease duration will be treated as missing.
 2. If the year is present but the month is missing, then the month will be treated as January for the calculation.

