7.11.5 Other Observations Related to Safety

7.11.5.1 Return of Menstrual Cycles

Analysis Set: Safety Analysis Set

Analysis

Variable(s) : Duration of Menstruation Recovery (Days)

Analytical

Method(s) : Summary (1) will be provided by treatment group.

(1) Summary of Duration of Menstruation Recovery

Descriptive statistics for observed values will be provided.

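### Duration of Menstruation Recovery pools women who stopped menstruating on treatment with women who kept cycling, so the placebo column and the difference between arms should not be read as recovery time

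*SAP*

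**What the plan says.** SAP 7.1.1 gives the formula: "Date of menstruation recovery - date of last dose of double-blind study drug". It sets no condition on menstrual status during treatment.

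Protocol 9.1.18 says which date is used: "If the first menstruation after the end of study drug administration is observed before the VISIT 7 in the Follow-up", the onset date goes into the eCRF. Otherwise contact continues after VISIT 7, as far as possible, until menstruation returns. This applies to any subject, suppressed or not. One group can be left without a date, because after the Follow-up period "follow-up will not be continued in subjects who undergo surgery or receive hormone therapy" before menstruation returns.

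SAP 7.11.5.1 takes the safety analysis set and states "Summary (1) will be provided by treatment group". The method is "Descriptive statistics for observed values will be provided". Under SAP 7.1, for a continuous variable, "the number of subjects with non-missing values, mean, median, SD, minimum, and maximum values will be tabulated". Under SAP 7.1.4, "No imputation of values for missing data will be performed unless otherwise specified". The table therefore covers every treated subject who has a recorded date, in both arms.

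Protocol 6.2.1 gives assessment of menstrual recovery as one reason for having the Follow-up period. Protocol 4.1 expects TAK-385 to produce amenorrhea. Protocol 9.1.17 has menstruation start and end dates entered in the CRF from the diary, which runs to the end of treatment.

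**The concern.** Recovery has meaning only for a woman whose menstruation had stopped. Entry requires regular cycles of 25 to 38 days (Protocol 7.1), and placebo is not expected to suppress them, so most placebo subjects should still be cycling at their last dose. For them the formula returns the days left until the next ordinary period. That number depends on cycle length and on the menstrual day on which VISIT 3 fell, and not on any return of function.

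Two misreadings could follow. A placebo mean of two to three weeks could be taken as a recovery time and set against the TAK-385 mean, although most of the placebo arm had nothing to recover from. And the TAK-385 column would combine true return of menses with residual cycle time from any woman who was not amenorrheic, without showing how many of each it contains. The table serves a stated purpose of the Follow-up, so it should be readable for that purpose.

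**Working it through.** The documents give no figure for menstrual recovery, so there is nothing of the plan's own to reproduce. The check asks what the SAP formula returns for a woman whose cycle is never disturbed.

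**Inputs**
- Cycle length L: 25 to 38 days (Protocol 7.1.3, criterion 13).
- Menstrual day k on which VISIT 3 (Day 1) falls: 1 to 5 (Protocol 6.1.1).
- Last dose: Day 84, from 12 weeks of dosing ending the day before VISIT 6 on Day 85.
- Assumptions, not in the documents: each subject's cycle length is constant, and all 14 × 5 = 70 combinations of L and k are equally likely.

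**Formula**
Menstruation starts on Day 1 − (k − 1) + mL, for m = 0, 1, 2, and so on. The SAP value is the first such day after Day 84, minus 84.

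**Worked cases**
- L = 28, k = 1: onsets on Days 1, 29, 57 and 85. Value 85 − 84 = 1 day.
- L = 28, k = 2: onsets on Days 0, 28, 56, 84 and 112 (a plain integer count, used here only for the arithmetic). Value 112 − 84 = 28 days.
- L = 28, k = 3, 4, 5: 27, 26, 25 days.
- L = 30, k = 1 to 5: 7, 6, 5, 4, 3 days.
- L = 38, k = 1 to 5: 31, 30, 29, 28, 27 days.

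With a 28-day cycle, moving VISIT 3 by one day changes the reported value from 1 to 28 days.

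**All 70 combinations**

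| Quantity | Result |
|---|---|
| Range | 1 to 31 days |
| Mean | 1196/70 = 17.1 days |
| Median | 18 days |
| Above 21 days | 24/70 = 34% |
| 25 days or more | 16/70 = 23% |

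**Sensitivity to constant cycles**
A simulation with a within-subject cycle SD of 2 days (also an assumption) gives mean 17.1, median 18 and a 5th to 95th percentile range of 3 to 30 days.

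**TAK-385 column**
If a fraction c of TAK-385 subjects with a date were still cycling, with mean about 17.1 days, and the rest had mean m, the column mean is 17.1c + (1 − c)m. It falls below m by c(m − 17.1) when m exceeds 17.1. The documents give neither c nor m for 40 mg, so this shift cannot be quantified.

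**Can the two kinds of subject be told apart?**
I applied a rule of no menstruation on Days 57 to 84 to the same 70 combinations with bleeds of 3, 5 and 7 days (70 × 3 = 210 cases). None of the 210 is classed as without menstruation, so the rule identifies regular cyclers correctly. It also follows that limiting the table to subjects without menstruation would leave the placebo column empty, or nearly so.

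**The case against.** The strongest defence is that the variable is exactly what Protocol 9.1.18 records: time from last dose to first menses. On that view the TAK-385 column answers the Follow-up question, and the placebo column is a natural reference for women not on active drug. On the grid no regular cycler exceeds 31 days, so longer TAK-385 times would point to delay beyond a normal cycle. Much of this stands. What it does not rescue is the label: a remainder of an ordinary cycle is presented as recovery, and nothing in the table says so.

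Three stronger readings are tempting, and the documents do not support them.
- A reader might infer that the duration is computed for every subject. It is not: only subjects with a recorded date contribute. The loss of the others is a separate matter.
- A reader might infer that the summary cannot show recovery at all. That goes too far, because the TAK-385 column still gives days to first menses in those with a date.
- A reader might expect about four weeks on placebo. The grid centres on 17 to 18 days; a figure near four weeks needs, for example, cycles close to 28 days with VISIT 3 after menstrual day 1.

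It can also be said that the eCRF recovery status or the Handling Rules for Analysis Data might already separate continuing cyclers. Neither was available here. The SAP points to no such rule for this variable.

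**Conclusion.** The point holds, at minor importance. The duration is summarised by arm for all safety-set subjects with a recorded first post-dose menstruation, whether or not menstruation had stopped. In women still cycling it measures residual cycle time, so neither the placebo column nor the between-arm difference is a recovery time. The TAK-385 column mixes two quantities in a proportion the documents do not let one estimate.

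The 1 to 31 day range and the mean of about 17 rest on stable, equally likely cycle lengths and menstrual days and on a last dose on Day 84; early stopping or irregular cycles would change individual values. That most placebo subjects keep cycling is an expectation from the entry criteria and the absence of active drug, not a figure in the documents.

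Menstrual recovery is not a listed endpoint, and the table is descriptive and untested. Sample size, type I error and the primary analysis are untouched.

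**What to change.** In SAP 7.1.1 and 7.11.5.1:
1. Use the CRF menstruation dates to classify each subject as with or without menstruation in the 28 days up to and including the last dose.
2. Report the number and percentage in each class by arm.
3. Summarise the duration separately by class within arm. Call it recovery only in subjects without on-treatment menstruation, and time to next menstruation in the others.

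A split is better than restricting the table to subjects without menstruation, because restriction would discard the placebo reference.

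The cost is SAP wording and one derived variable from data already collected. The drawbacks are small cells, with about 32 subjects per arm divided in two, and classes defined by a post-randomisation outcome. The split is therefore descriptive only, and comparisons between arms within a class do not carry the protection of randomisation. A subject with an unusually long or irregular cycle may be misclassified.
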